APPENDIX VIII: BLOOD PRESSURE LEVELS FOR CHILDREN BY AGE AND HEIGHT PERCENTILE
Blood pressure (BP) levels for BOYS

Age (years)	BP Percentile	Systolic Blood Pressure, mm Hg							Diastolic Blood Pressure, mm Hg						
		Percentile of Height						Percentile of Height							
		5th	10th	25th	50th	75th	90th	95th	5th	10th	25th	50th	75th	90th	95th
1	95th	98	99	101	103	104	106	106	54	54	55	56	57	58	58
2	95th	101	102	104	106	108	109	110	59	59	60	61	62	63	63
3	95th	104	105	107	109	110	112	113	63	63	64	65	66	67	67
4	95th	106	107	109	111	112	114	115	66	67	68	69	70	71	71
5	95th	108	109	110	112	114	115	116	69	70	71	72	73	74	74
6	95th	109	110	112	114	115	117	117	72	72	73	74	75	76	76
7	95th	110	111	113	115	117	118	119	74	74	75	76	77	78	78
8	95th	111	112	114	116	118	119	120	75	76	77	78	79	79	80
9	95th	113	114	116	118	119	121	121	76	77	78	79	80	81	81
10	95th	115	116	117	119	121	122	123	77	78	79	80	81	81	82
11	95th	117	118	119	121	123	124	125	78	78	79	80	81	82	82
12	95th	119	120	122	123	125	127	127	78	79	80	81	82	82	83
13	95th	121	122	124	126	128	129	130	79	79	80	81	82	83	83
14	95th	124	125	127	128	130	132	132	80	80	81	82	83	84	84
15	95th	126	127	129	131	133	134	135	81	81	82	83	84	85	85
16	95th	129	130	132	134	135	137	137	82	83	83	84	85	86	87
≥17	95th	131	132	134	136	138	139	140	84	85	86	87	87	88	89

Instructions for using this BP Chart:

1. Measure the patient's blood pressure using an appropriate size cuff.
2. Select appropriate chart for a female or male patient.
3. Using the "age" row and "height" column determine if the BP is within the ULN.
4. See [Section 5.5.1](#) for definition of dose limiting hypertension, [Section 6.4](#) for management and grading of hypertension, and [Section 7.7](#) for medical treatment of ramucirumab related hypertension.

This table was taken from "The Fourth Report on the Diagnosis, Evaluation, and Treatment of High Blood Pressure in Children and Adolescents" [PEDIATRICS](#) Vol. 114 No. 2 August 2004, pp. 555-576.

Blood pressure (BP) levels for GIRLS

Age (years)	BP Percentile	Systolic Blood Pressure, mm Hg							Diastolic Blood Pressure, mm Hg						
		Percentile of Height							Percentile of Height						
		5th	10th	25th	50th	75th	90th	95th	5th	10th	25th	50th	75th	90th	95th
1	95th	100	101	102	104	105	106	107	56	57	57	58	59	59	60
2	95th	102	103	104	105	107	108	109	61	62	62	63	64	65	65
3	95th	104	104	105	107	108	109	110	65	66	66	67	68	68	69
4	95th	105	106	107	108	110	111	112	68	68	69	70	71	71	72
5	95th	107	107	108	110	111	112	113	70	71	71	72	73	73	74
6	95th	108	109	110	111	113	114	115	72	72	73	74	74	75	76
7	95th	110	111	112	113	115	116	116	73	74	74	75	76	76	77
8	95th	112	112	114	115	116	118	118	75	75	75	76	77	78	78
9	95th	114	114	115	117	118	119	120	76	76	76	77	78	79	79
10	95th	116	116	117	119	120	121	122	77	77	77	78	79	80	80
11	95th	118	118	119	121	122	123	124	78	78	78	79	80	81	81
12	95th	119	120	121	123	124	125	126	79	79	79	80	81	82	82
13	95th	121	122	123	124	126	127	128	80	80	80	81	82	83	83
14	95th	123	123	125	126	127	129	129	81	81	81	82	83	84	84
15	95th	124	125	126	127	129	130	131	82	82	82	83	84	85	85
16	95th	125	126	127	128	130	131	132	82	82	83	84	85	85	86
≥17	95th	125	126	127	129	130	131	132	82	83	83	84	85	85	86

Instructions for using this BP Chart:

1. Measure the patient's blood pressure using an appropriate size cuff.
2. Select appropriate chart for a female or male patient.
3. Using the "age" row and "height" column determine if the BP is within the ULN.
4. See [Section 5.5.1](#) for definition of dose limiting hypertension, [Section 6.4](#) for management and grading of hypertension, and [Section 7.7](#) for medical treatment of ramucirumab related hypertension.

This table was taken from "The Fourth Report on the Diagnosis, Evaluation, and Treatment of High Blood Pressure in Children and Adolescents" PEDIATRICS Vol. 114 No. 2 August 2004, pp. 555-576.

APPENDIX IX: URINE PROTEIN TO CREATININE (UPC) RATIO**Clinical Meaning of UPC**

There is a good correlation between the ratio of urine protein to creatinine concentrations (UPC) in a random urine sample and the amount of protein excreted in a 24-hour urine collection period.⁸³ Thus, the UPC allows for an estimation of the 24-hour urine protein excretion from a random sample. The creatinine excretion is fairly constant throughout the day regardless of changes in urine flow rate:

- Men excrete 20 mg to 25 mg of creatinine/kg of body weight/day
- Women excrete 15 mg to 20 mg of creatinine/kg of body weight/day
- Normal protein excretion is <100 mg to 150 mg per 24 hours.
- The UPC ratio is roughly equal to the 24 hour urine protein excretion in g/day

Calculating UPC Ratio

UPC ratio = (Urine protein [mg/dL]) / (urine creatinine [mg/dL]) = numerically equivalent to grams (g) protein excreted in urine over 24 hours.

Example: If a subject has a urine protein of 90 mg/dL and urine creatinine of 30 mg/dL,

$$\text{then UPC ratio} = \frac{90 \text{ (mg/dL)}}{30 \text{ (mg/dL)}} = 3$$

Result UPC is 3 correlating to roughly 3g of protein excretion in a 24-hour period.

Units for UPC ratio

UPC is a calculated ratio. The guidelines in the protocol are based on having urine protein and urine creatinine measured in the same units (e.g., mg/dL). The SI units for urine protein and urine creatinine are not the same, so these must be converted to mg/dL before calculating the ratio. For reference, the conversion factors for commonly used units for protein and creatinine are provided below.

Starting units	Conversion to mg/dL
Protein (g/L)	Multiply by 100
Creatinine (μmol/L)	Divide by 88.4
Creatinine (mmol/L)	Multiply by 11.3

APPENDIX X: TOXICITY-SPECIFIC GRADING

Bilirubin

Grade 1:	$> \text{ULN} \leq 1.5 \times \text{ULN}$
Grade 2:	$> 1.5 \times \text{ULN} - 3.0 \times \text{ULN}$
Grade 3:	$> 3.0 \times \text{ULN} - 10.0 \times \text{ULN}$
Grade 4:	$> 10.0 \times \text{ULN}$

ALT: For the purpose of this study, the ULN for SGPT is 45 U/L regardless of baseline.

Grade 1:	$> 45 \text{ U/L} \leq 135 \text{ U/L}$
Grade 2:	$136 \text{ U/L} - 225 \text{ U/L}$
Grade 3:	$226 \text{ U/L} - 900 \text{ U/L}$
Grade 4:	$> 900 \text{ U/L}$

AST: For the purpose of this study, the ULN for SGOT is 50 U/L regardless of baseline.

Grade 1:	$> 50 \text{ U/L} \leq 150 \text{ U/L}$
Grade 2:	$151 \text{ U/L} - 250 \text{ U/L}$
Grade 3:	$251 \text{ U/L} - 1000 \text{ U/L}$
Grade 4:	$> 1000 \text{ U/L}$

GGT:

Grade 1:	$> \text{ULN} - 2.5 \times \text{ULN}$
Grade 2:	$> 2.5 \times \text{ULN} - 5.0 \times \text{ULN}$
Grade 3:	$> 5.0 \times \text{ULN} - 20.0 \times \text{ULN}$
Grade 4:	$> 20.0 \times \text{ULN}$

APPENDIX XI: CTEP AND CTSU REGISTRATION PROCEDURES

Food and Drug Administration (FDA) regulations and National Cancer Institute (NCI) policy require all individuals contributing to NCI-sponsored trials to register and to renew their registration annually. To register, all individuals must obtain a Cancer Therapy Evaluation Program (CTEP) Identity and Access Management (IAM) account (<https://ctepcore.nci.nih.gov/iam>). In addition, persons with a registration type of Investigator (IVR), Non-Physician Investigator (NPIVR), or Associate Plus (AP) (i.e., clinical site staff requiring write access to OPEN, RAVE, or TRIAD or acting as a primary site contact) must complete their annual registration using CTEP's web-based Registration and Credential Repository (RCR) (<https://ctepcore.nci.nih.gov/rcr>). Documentation requirements per registration type are outlined in the table below.

Documentation Required	IVR	NPIVR	AP	A
FDA Form 1572	✓	✓		
Financial Disclosure Form	✓	✓	✓	
NCI Biosketch (education, training, employment, license, and certification)	✓	✓	✓	
HSP/GCP training	✓	✓	✓	
Agent Shipment Form (if applicable)	✓			
CV (optional)	✓	✓	✓	

An active CTEP-IAM user account and appropriate RCR registration is required to access all CTEP and CTSU (Cancer Trials Support Unit) websites and applications. In addition, IVRs and NPIVRs must list all clinical practice sites and IRBs covering their practice sites on the FDA Form 1572 in RCR to allow the following:

- Added to a site roster
- Assigned the treating, credit, consenting, or drug shipment (IVR only) tasks in OPEN
- Act as the site-protocol PI on the IRB approval
- Assigned the Clinical Investigator (CI) role on the Delegation of Tasks Log (DTL).

Additional information can be found on the CTEP website at <<https://ctep.cancer.gov/investigatorResources/default.htm>>. For questions, please contact the RCR **Help Desk** by email at <[contact]>.

CTSU Registration Procedures

This study is supported by the NCI Cancer Trials Support Unit (CTSU).

IRB Approval:

Each investigator or group of investigators at a clinical site must obtain IRB approval for this protocol and submit IRB approval and supporting documentation to the CTSU Regulatory Office before they can be approved to enroll patients. Assignment of site registration status in the CTSU Regulatory Support System (RSS) uses extensive data to make a determination of whether a site has fulfilled all regulatory criteria including but not limited to the following:

- An active Federal Wide Assurance (FWA) number
- An active roster affiliation with the Lead Network or a participating organization
- A valid IRB approval
- Compliance with all protocol specific requirements.

In addition, the site-protocol Principal Investigator (PI) must meet the following criteria:

- Active registration status
- The IRB number of the site IRB of record listed on their Form FDA 1572
- An active status on a participating roster at the registering site.

ites participating on the NCI CIRB initiative that are approved by the CIRB for this study are not required to submit IRB approval documentation to the CTSU Regulatory Office. For sites using the CIRB, IRB approval information is received from the CIRB and applied to the RSS in an automated process. Signatory Institutions must submit a Study Specific Worksheet for Local Context (SSW) to the CIRB via IRBManager to indicate their intent to open the study locally. The CIRB's approval of the SSW is then communicated to the CTSU Regulatory Office. In order for the SSW approval to be processed, the Signatory Institution must inform the CTSU which CIRB-approved institutions aligned with the Signatory Institution are participating in the study.

Requirements For ADVL1416 Site Registration:

- IRB approval (For sites not participating via the NCI CIRB; local IRB documentation, an IRB-signed CTSU IRB Certification Form, Protocol of Human Subjects Assurance Identification/IRB Certification/Declaration of Exemption Form, or combination is accepted)
- For applicable studies with a radiation and/or imaging (RTI) component, the enrolling site must be aligned to a RTI provider. To manage provider associations access the Provider Association tab on the CTSU website at <https://www.ctsu.org/RSS/RTFProviderAssociation>, to add or remove associated providers. Sites must be linked to at least one IROC credentialed provider to participate on trials with an RT component. Enrolling sites are responsible for ensuring that the appropriate agreements are in place with their RTI provider, and that appropriate IRB approvals are in place.

THIS PROTOCOL IS FOR RESEARCH PURPOSES ONLY, SEE PAGE 1 FOR USAGE POLICY

Submitting Regulatory Documents:

Submit required forms and documents to the CTSU Regulatory Office, where they will be entered and tracked in the CTSU RSS.

Regulatory Submission Portal: www.ctsu.org (members' area) → Regulatory Tab → Regulatory Submission

When applicable, original documents should be mailed to:
CTSU Regulatory Office

[name]
[name]

Institutions with patients waiting that are unable to use the Portal should alert the CTSU Regulatory Office immediately at [name] in order to receive further instruction and support.

### **3. Revision History**

Statistical Analysis Plan (SAP) Version 1 was approved prior to final analysis of the study.

## 4. Study Objectives

### 4.1. Primary Objective

The primary objectives of the study are as follows:

- to estimate the maximum tolerated dose (MTD) and/or recommended Phase 2 dose (RP2D) of ramucirumab administered as an intravenous (IV) infusion over 60 minutes, every 2 weeks, to children with recurrent or refractory solid tumors
- to determine the tolerability of the MTD and/or RP2D of ramucirumab in children with recurrent or refractory central nervous system (CNS) tumors
- to define and describe the toxicities of ramucirumab administered on this schedule
- to characterize the pharmacokinetics (PK) and immunogenicity of ramucirumab in children with recurrent or refractory solid tumors including CNS tumors

### 4.2. Secondary Objectives

The secondary objective of the study is as follows:

- to preliminarily define the antitumor activity of ramucirumab within the confines of a Phase 1 study

### 4.3. Exploratory Objectives

The exploratory objectives of the study are as follows:

- to explore the pharmacodynamics (PD) effects of ramucirumab in this pediatric population
- to explore potential predictive biomarkers relevant to pediatric cancers, cancer-related conditions, ramucirumab and angiogenesis

## 5. Study Design

### 5.1. Summary of Study Design

The study will be completed in 2 parts. Part A will be a safety and dose-finding phase of the study for patients with non-CNS solid tumors, and will include dose-escalation and dose-expansion components. Part B will include a safety evaluation specifically for patients with CNS tumors.

For the dose-escalation phase, a rolling 6 design will be used. Starting dose will be 8 mg/kg IV every 2 weeks (Q2W) with 3 doses per 42 day cycle (Dose Level 1). The decision rules of dose level assignment based on dose-limiting toxicity (DLT) are introduced in the section below. If the MTD is not exceeded (0 or 1 DLT/6 fully evaluable patients) at 8 mg/kg dose level, a second dose level will be explored at the escalated dose of 12 mg/kg IV Q2W with 3 doses per cycle (Dose Level 2). After accrual to Dose Level 2 is completed, PK comparisons from dose levels 1 and 2 will be performed. The goal is to expand at the dose level at which at least 5 out of 6 patients achieve a day 42  $C_{min} \geq 50 \mu\text{g/mL}$ . If PK analysis indicates that more than 1 patient treated at 12 mg/kg dose level has a day 42  $C_{min}$  significantly less than 50  $\mu\text{g/mL}$ , and the MTD has not been exceeded, additional dose levels will be considered. If the MTD in children and adolescents is exceeded at 8 mg/kg IV Q2W, de-escalation to 6 mg/kg will be considered, and the recommended dose will be based on the MTD.

An expansion cohort will accrue at the lowest tolerable dose at which  $C_{min}$  of  $\geq 50 \mu\text{g/mL}$  has been achieved in at least 5 out of 6 evaluable patients, to acquire PK data in a representative number of young patients (ie, patients <12 years old). If at least 10 out of the total of 12 evaluable patients have a steady state concentration of ramucirumab greater than 50  $\mu\text{g/mL}$ , then the RP2D has been defined.

### 5.2. Determination of Sample Size

The primary objective for the dose-escalation phase and the dose-expansion cohort in Part A is to evaluate safety and tolerability in patients with non-CNS solid tumors for the purpose of determining a RP2D; the primary objective in Part B is to evaluate safety in patients with CNS tumors at dose selected as the RP2D in Part A. The sample size of each part of the study is selected to allow adequate assessment of safety at the recommended dose for ramucirumab.

#### Part A:

A minimum of 2 evaluable patients will be entered at each dose level for determination of MTD. Once the MTD or RP2D has been defined, up to 6 additional patients with recurrent or refractory solid tumors without restrictions on hematologic evaluability may be enrolled to acquire PK data in a representative number of young patients. The anticipated maximum number of evaluable subjects required to complete Part A is 24 patients. Assuming a 20% inevaluable rate, 29 patients may be enrolled.

#### Part B:

Once the RP2D has been determined in Part A, Part B will open to enroll children with relapsed or refractory CNS tumors who will receive ramucirumab at the MTD or RP2D. Part B of the study will require up to 6 evaluable patients enrolled at the MTD/RP2D as determined in Part A. Allowing for 20% inevaluability, 8 patients may be enrolled.

### 5.3. Method of Assignment to Dose Level

In the rolling 6 study design, 2 to 6 patients can be concurrently enrolled onto a dose level, based on the number of patients currently enrolled in the cohort, the number of DLTs observed, and the number of patients at risk for developing a DLT. Accrual is suspended when a cohort of 6 has enrolled or when the study endpoints have been met.

**Table JVDA.1** provides the decision rules for enrolling a patient at (i) the current dose level (ii) at an escalated dose level, (iii) at a de-escalated dose level, or whether the study is suspended to accrual. For example, when 3 patients are enrolled onto a dose cohort, if toxicity data is available for all 3 when the fourth patient entered and there are no DLTs, the dose is escalated and the fourth patient is enrolled to the subsequent dose level. If data is not yet available for 1 or more of the first 3 patients and no DLT has been observed, or if one DLT has been observed, the new patient is entered at the same dose level. Lastly, if 2 or more DLTs have been observed, the dose level is de-escalated. If the dose for the fourth patient is escalated, another patient will be enrolled in the subsequent dose level and restart the decision rules for the new dose level.

**Table JVDA.1. Dose Level Decision Rules in Rolling 6 Design**

# Pts Enrolled	# Pts with DLT	# Pts without DLT	# Pts with Data Pending	Decision
2	0 or 1	0, 1 or 2	0, 1 or 2	Same dose level
2	2	0	0	De-escalate a
3	0	0, 1 or 2	1, 2 or 3	Same dose level
3	1	0, 1 or 2	0, 1 or 2	Same dose level
3	0	3	0	Escalate b
3	≥ 2	0 or 1	0 or 1	De-escalate a
4	0	0, 1, 2 or 3	1, 2, 3 or 4	Same dose level
4	1	0, 1, 2 or 3	0, 1, 2 or 3	Same dose level
4	0	4	0	Escalate b
4	≥ 2	0, 1 or 2	0, 1 or 2	De-escalate a
5	0	0, 1, 2, 3 or 4	1, 2, 3, 4 or 5	Same dose level
5	1	0, 1, 2, 3 or 4	0, 1, 2, 3 or 4	Same dose level
5	0	5	0	Escalate b
5	≥ 2	0, 1, 2 or 3	0, 1, 2 or 3	De-escalate a
6	0	0, 1, 2, 3, or 4	2, 3, 4, 5 or 6	Suspend
6	1	0, 1, 2, 3 or 4	0, 1, 2, 3 or 4	Suspend
6	0 or 1	5 or 6	0 or 1	Escalate b
6	≥ 2	0, 1, 2, 3 or 4	0, 1, 2, 3 or 4	De-escalate a

Abbreviations: DLT = dose-limiting toxicity; MTD = maximum tolerated dose; Pts = patients.

a If six patients already entered at next lower dose level, the MTD has been defined.

b If final dose level has been reached, the recommended dose has been reached.

## 6. A Priori Statistical Methods

Statistical analysis of this study will be the responsibility of Eli Lilly and Company or its designee. The study PK scientist will be responsible for designing, conducting, and interpreting the PK analysis and delivering PK parameters. The interpretation of final study results will be the responsibility of the clinical research physician (CRP) and the study statistician.

Exploratory statistical analysis procedures not specified in the present document will be executed as deemed appropriate by the statistician and study team.

The following general terms will be used globally in the SAP:

- Unless otherwise specified, summary statistics stand for the number of patients with an observation (n), mean, standard deviation, median, minimum, and maximum for continuous variables; and population size (N), the number of events, the number of subjects with events (n) and the proportion of subjects with events ( $p=n/N$ ) for categorical variables.
- **Safety population** will consist of subjects who receive any amount of study drug. The safety population will be used for all analyses of dosing, exposure and safety.
- **DLT-evaluable population** will consist of: 1) subjects who receive at least 1 dose of the study drug and then experience DLT during Cycle 1; and 2) subjects who receive at least 85% of the prescribed dose in Cycle 1 and have an adverse event (AE) assessment in the first cycle. Dose-limiting toxicity-evaluation population will be used for evaluation of each dose level for dose-escalation.
- **Pharmacokinetic population** will include subjects who have sufficient PK data to derive at least one PK parameter.
- **Efficacy population** will include all patients who receive any quantity of study treatment at the dose recommended.

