Eight anti-angiogenic agents have completed Phase-1 clinical testing in children: bevacizumab,³⁶ afibbercept,³⁷ and several VEGFR-2 TKIs, including cediranib,³⁸ pazopanib,³⁹ semaxanib,⁴⁰ sereferib,⁴¹ sunitinib,⁴² and vandetanib.⁴³ Compared to adult recommended dosing, those for children have ranged from reduced dosing in pediatrics, due to MTDs seen in many of the TKIs and afibbercept, to pediatric dosing that is comparable to adult dosing, as is the case for bevacizumab where an MTD was never established in the pediatric population.¹⁶ Safety profiles of anti-angiogenics have been similar across age groups, with class effects including hypertension, proteinuria, and arterial thrombo-embolic events.¹⁶ For children, two potential toxicities of particular interest are growth plate abnormalities and cardiotoxicity, given the prevalent use of anthracyclines in pediatric regimens. Physeal widening was observed in a single anti-angiogenic phase 1 trial with pazopanib; no other pediatric studies of VEGF pathway inhibitors have reported growth plate defects. Cardiotoxicities have been observed in some patients with prior anthracycline exposure who were treated with anti-angiogenic agents, though the pathogenesis of this cardiotoxicity and its association with VEGF pathway inhibition is not yet known. Regarding efficacy, while there is minimal data on

THIS PROTOCOL IS FOR RESEARCH PURPOSES ONLY, SEE PAGE 1 FOR USAGE POLICY

the anti-tumor activity of commonly used anti-angiogenic agents in children, single agent activity consisting of partial responses and stable disease have been reported in patients with soft-tissue sarcoma, Ewing's sarcoma, osteosarcoma, Wilm's tumor, hepatoblastoma, ependymoma, and gliomas.³⁵

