8.2 Monitoring for Specific Toxicities

8.2.1 Growth Plate Toxicity

Patients will have a plain AP radiograph of a single proximal tibial growth plate obtained prior to the first dose of protocol therapy.

- a. If patients are found to have a closed tibial growth plate, no further radiographs will be required.
- b. If patients are found to have an open tibial growth plate, then repeat plain AP radiographs of the same tibial growth plate will be obtained prior to cycles 2, 5 and every 6 months.
 - Patients with evidence of growth plate thickening or other changes should have a knee MRI performed to further assess the degree of physeal pathology and undergo more frequent x-ray follow up at least every 3 cycles or as clinically indicated. MRI should be performed without contrast.
 - Patients with knee MRI changes should be managed in an individualized manner. Decisions regarding continuation of ramucirumab should be

THIS PROTOCOL IS FOR RESEARCH PURPOSES ONLY, SEE PAGE 1 FOR USAGE POLICY

made after discussion with the Study Chair or Study Vice-Chair and DVL Leadership, taking into account the presence of any symptoms referable to the knee as well as the patient's response to ramucirumab. Consultation with an orthopedic surgeon may also be indicated. Plans for follow-up imaging will also be made on an individualized basis, taking into account the presence of symptoms at the knee or other joints as well as the decision to continue ramucirumab or not.

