11.6 Statistical methods

11.6.1 **Analysis Sets**

Safety Analysis Set (SAS) will consist of subjects who receive any amount of study drug.

11.6.2 **Dose Evaluable Set (DES)** will consist of: 1) subjects who receive any amount of study drug and then experience DLT during Cycle 1; and 2) subjects who receive at least 85% of the prescribed dose in Cycle 1 and have an adverse event assessment in the first cycle. DES will be used for evaluation of each dose level for dose-escalation.

11.6.3 **Pharmacokinetic Analysis Set (PAS)** will include subjects who have sufficient PK data to derive at least one PK parameter.

11.6.4 **Efficacy Analyses:**

Preliminary efficacy analyses will also be performed by dose cohort for the Safety Analysis Set. Data cut-off for primary study analysis will occur when all enrolled subjects have completed 6 cycles of treatment or discontinued study drug administration. After the final analysis, additional analyses may be performed as appropriate.

11.6.5 **Pharmacokinetic Analyses**

Serum concentrations of Ramucirumab will be tabulated and summarized by dose level and time. Ramucirumab PK parameters will be derived from serum concentrations by non-compartmental analyses using actual times. Minimally, the following PK parameters will be calculated: C_{max} , t_{max} , and $AUC (t_{1/2}, CL, and Vd_{ss})$ will be calculated only if the data permit). Additional analysis utilizing the population pharmacokinetic approach may also be conducted if deemed appropriate.

11.6.6 **Immunogenicity Analyses**

Immunogenicity incidence will be tabulated, and correlation of immunogenicity to ramucirumab drug level, activity, and safety will be assessed as appropriate.

11.6.7 **Statistical Analyses**

Baseline demographics and baseline disease characteristics will be summarized for all enrolled patients who had at least one dose of study therapy.

Listing of patients including those treated at the MTD will be generated.

Treatment-emergent CTCAEs will be summarized by each dose level and for

THIS PROTOCOL IS FOR RESEARCH PURPOSES ONLY, SEE PAGE 1 FOR USAGE POLICY

overall population by each CTCAE grade separately.

Best overall response, duration of response, and duration of stable disease will also be summarized descriptively by each dose level.

Listing of deaths on study or 30 day post-discontinuation will be provided. Listing of SAEs will also be produced. Listing of AEs leading to treatment discontinuation will be provided.

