## 6.7. Safety Analyses

All patients who receive at least 1 dose of study therapy will be summarized for safety and toxicity. Dose-limiting toxicity will be listed for Phase 1a only by ramucirumab dose schedules. Please refer to the protocol for the definition of DLT.

The descriptions and grading scales found in the revised National Cancer Institute (NCI) Common Terminology Criteria for Adverse Events (CTCAE) version 4.0 will be utilized for AE reporting. Unless otherwise specified, when summarized by Preferred Term (PT), AEs will be presented in decreasing frequency of PT across dose levels; when summarized by System Organ Class (SOC) and PT, AEs will be presented in decreasing frequency of PT within SOC across dose levels.

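### Under the SAP's default rule, growth-plate findings would be expressed over all treated patients, although only those with an open tibial plate at baseline are followed for them

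*SAP*

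**What the plan says.** **Analysis population.** SAP 6 defines the safety population as patients who receive any study drug and adds: "The safety population will be used for all analyses of dosing, exposure and safety". SAP 6.7 repeats the point: "All patients who receive at least 1 dose of study therapy will be summarized for safety and toxicity".

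**Denominator.** Unless something else is specified, SAP 6 summarises events by the population size N, the number of subjects with the event n, and "the proportion of subjects with events ( $p=n/N$ ) for categorical variables".

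**Exceptions.** None is specified for growth plates. The SAP does not mention them. SAP 6.7.3 plans summaries of events of special interest but lists no terms. SAP 6.3 does not include plate status among the baseline characteristics. Protocol 11.6.7 summarises toxicity only by dose level and overall.

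**Ascertainment.** Protocol 8.1 (footnote 7) and 8.2.1 require a tibial film in every patient before the first dose. Protocol 8.2.1 then divides the patients: "If patients are found to have a closed tibial growth plate, no further radiographs will be required". Those with an open plate have repeat films before cycles 2 and 5 and every 6 months, with a knee MRI if the film shows change.

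**Importance.** Protocol 2.1 says that, for children, "two potential toxicities of particular interest are growth plate abnormalities and cardiotoxicity".

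**The concern.** A patient whose plate is closed at baseline has no further scheduled films, so growth-plate surveillance cannot record an event in that patient. Under the default rule the patient still counts in N as event-free. The proportion then mixes two things: how often the toxicity occurs in patients with an open plate, and how many treated patients had one.

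Closed plates are foreseeable. Protocol 4.1.1 admits patients up to 21 years, and Protocol 8.2.1 has a rule for closed plates. The share may also differ between dose levels, because the expansion cohort is aimed at patients under 12. All-treated rates at two dose levels could therefore differ through age mix alone.

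Describing the toxicities is a primary aim. Protocol 2.4.1 reports no earlier paediatric experience with the drug, and the chronic monkey study in Protocol 2.2.2 found growth-plate thickening at every dose. A later reader will want the risk for a child who is still growing. The planned summaries would not give it, and a zero count would look more reassuring than the number of patients actually followed allows.

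**Working it through.** **Inputs**
- Default rule: p = n/N with N = all treated patients (SAP 6 and 6.7).
- Follow-up films only for patients with an open plate at baseline (Protocol 8.2.1).
- Illustrative cohort of 12 at the recommended dose. Protocol 11.1 gives six under 12 years and six aged 12 or over as an example.
- Closed-plate share c: not in the documents, so assumed and shown as a range.

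**The plan's own figures.** No growth-plate rate or open-plate count is stated, so there is none to reproduce. The nearest planned denominator is Part A: 3 dose levels × 6 + 6 expansion patients = 24 evaluable, and 24 × 1.2 = 28.8, giving the stated 29 enrolled.

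**Formula.** Let x be the number of patients with a growth-plate finding, all of them with an open plate at baseline. Let N_open be the number with an open plate, so c = (N − N_open)/N. Then

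x/N = (x/N_open) × (N_open/N) = (1 − c) × x/N_open.

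The all-treated proportion is thus lower than the open-plate incidence by the relative factor c. The gap in percentage points is c × x/N_open.

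**One event among 12 treated patients (all-treated rate 1/12 = 8.3%)**

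| Closed (assumed) | Open | c | Rate over open-plate patients |
|---|---|---|---|
| 0 | 12 | 0 | 1/12 = 8.3% |
| 1 | 11 | 0.08 | 1/11 = 9.1% |
| 3 | 9 | 0.25 | 1/9 = 11.1% |
| 4 | 8 | 0.33 | 1/8 = 12.5% |
| 6 | 6 | 0.50 | 1/6 = 16.7% |
| 8 | 4 | 0.67 | 1/4 = 25.0% |

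Check for the row with 4 closed: (1 − 4/12) × 12.5% = 8.3%.

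**Zero events.** The one-sided 95% upper limit is 1 − 0.05^(1/n). For n = 12 it is 22.1%; for n = 8 it is 31.2%. The SAP plans no such limits for adverse-event rates. The comparison only shows how much less information 8 followed patients carry than 12.

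**Films after baseline.** The schedule table in Protocol 8.1 marks a tibial radiograph at the off-therapy visit, 30 days after the last dose. Footnote 7 to that table refers follow-up films to Protocol 8.2.1, which does not list an off-therapy film. On the table, an open-plate patient who stops during cycle 1 still has a film due; on 8.2.1 alone, that patient may have none.

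**The case against.** **No growth-plate table is planned.** A reader might infer that the SAP commits itself to a growth-plate rate over all treated patients. It does not; that denominator follows from a general default, and SAP 6 leaves room for further analyses that the team judges appropriate. This limits the wording of the point but does not remove it. Permission to do something else is not a stated denominator, and the default governs until an exception is written.

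**SAP 6.9 already refers to patients at risk.** The registry tables are to give the number at risk for each event term. The wording is generic, does not define risk by plate status, and concerns registry output. It shows that a term-specific denominator fits the plan; it does not supply one. The documents accept the principle elsewhere: Protocol 4.1.7.1 treats patients with marrow disease as not evaluable for hematologic toxicity, and SAP 6.5.2 restricts best response to patients assessable by RECIST.

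**The all-treated proportion is not wrong.** This stands. It answers how many treated patients had the event. It misleads only if read as the risk for a patient with an open plate.

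**The size is assumed.** This also stands. A reader might infer from the age range and the six/six split that a large share of patients will have closed plates. The split is only an example, being 12 or older is not the same as having a closed plate, and Protocol 5.3.1 and 11.2.3 and SAP 5.1 aim the expansion at patients under 12.

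**Early leavers.** A reader might infer that open-plate patients who stop before cycle 2 are never re-imaged and dilute the rate further. The off-therapy film marked in Protocol 8.1 prevents that conclusion. How many go without a film is unknown until the two passages are reconciled and the re-imaged count is reported.

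**Consequence.** The safety reporting is descriptive, adverse events and demographics are listed by patient, and every patient has a baseline film. The open-plate rate could be produced later. That makes the fix cheap; it does not justify leaving the denominator to be chosen after the events are known.

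**Conclusion.** The point holds as a gap in the SAP. If the default rule is followed, a growth-plate rate would be (1 − c) times the rate in patients with an open plate at baseline. For one event in 12, that is 8.3% against 12.5% if 4 of the 12 have closed plates, with a range from 8.3% (none closed) to 25.0% (8 closed). These figures assume that scheduled surveillance detects events only in open-plate patients, and c itself is an assumption throughout.

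The documents do not support the stronger statements that a biased table is planned, that the all-treated proportion is incorrect, or that the size of the shortfall is known. The change affects neither the DLT-evaluable population nor the RP2D rule. It is worth making because the protocol singles out this toxicity in children and the cost is very small.

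**What to change.** 1. **SAP 6.3:** add baseline tibial plate status (open or closed) to the baseline characteristics.
2. **SAP 6.7:** report growth-plate findings on radiograph and knee MRI, by dose level and overall, with N = patients with an open tibial plate at baseline.
3. **Same table:** show the number closed at baseline, the number open with at least one post-baseline film and the rate in that subset, the number open but not re-imaged, and the all-treated N. The main denominator should be open at baseline, because requiring a later film could select patients who stayed on treatment longer. The re-imaged rate beside it shows the effect of missing films.
4. **Other adverse events:** keep the safety population.
5. **Protocol 8.1 and 8.2.1:** reconcile the two passages on the off-therapy radiograph, so that it is clear which films count as follow-up.

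The cost is a short addition to the SAP and one small table, from films the protocol already requires. The downside is a smaller N and a slightly less favourable rate.
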